### 6.3.3 Logistics

Recruitment rate will be represented graphically by plotting monthly recruitment and cumulative recruitment numbers at each month of active recruitment. Proportions and 95% confidence intervals for screened patients eligible for run-in and eligible patients who entered run-in will be estimated as described above for tolerability outcome variables. Proportions randomised to carvedilol and placebo on a 25 mg dose during each titration and follow-up visit will be separately analysed for each treatment group using a mixed-effects logistic regression model with study visit as a fixed effect in the model and participant identifier as a random effect. Proportions on each dose of study drug (6.25 mg, 12.5 mg, 25 mg) by treatment group across titration and follow-up visits will be described.

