### **1.2 Study synopsis**

The BLOCADE trial is a feasibility study for a large multi-centre, randomised, placebo-controlled trial of the effectiveness of the beta-blocker carvedilol to reduce cardiovascular morbidity and mortality in high-risk patients receiving dialysis. The multi-centre feasibility study had a six week active run-in period during which all participants received carvedilol. After the run-in period participants who tolerated carvedilol were randomised 1:1 to receive carvedilol (experimental intervention) or placebo (control intervention).

The BLOCADE feasibility study began recruiting patients on 16 May 2011 and stopped recruiting on 28 February 2013 due to slow recruitment and lack of funds to continue recruiting participants. In total, 88 participants from 11 sites were consented into the study. Of these, 72 participants from 9 sites entered the run-in phase and 49 participants from 8 sites were randomised. The final end-of-study visit was conducted in June 2014. The central database is expected to be available for analysis by the end of June 2014.

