### 3.2.2 Exclusion criteria

Patients were excluded from the study if any one of the following conditions was met:

- 1) Scheduled for live donor transplant within six months.
- 2) Experienced a cardiovascular event in the previous 3 months. Cardiovascular events include: myocardial infarction, admission for unstable angina, coronary revascularisation procedure, peripheral arterial revascularisation procedure or stroke.
- 3) Definite contra-indication to beta-blockers, such as:
  - a) 2nd or 3rd degree atrioventricular block unless treated with a permanent pacemaker
  - b) sick sinus syndrome unless treated with a permanent pacemaker
  - c) clinically significant reversible bronchospasm
  - d) previous intolerance to beta-blockers
  - e) other contra-indication
- 4) Currently taking a **beta-blocker, verapamil, diltiazem or moxonidine** and the treating nephrologist does not wish to stop these medications in order to enter the trial.
- 5) Considered by the treating nephrologist to be clinically or haemodynamically unstable for the study.
- 6) Unstable target weight (defined by a change of  $\geq 2.0$ kg in target base weight over the preceding month).
- 7) Severe hepatic dysfunction (transaminases  $\geq 3$ x higher than the upper normal limit) on the most recent liver function tests (if performed within 3 months).
- 8) Already involved in a clinical trial where the intervention being trialled is likely to confound the outcome of this trial.
- 9) Considered by the treating physician to have a life expectancy of less than 12 months.
- 10) Inability to provide consent or follow study instructions due to psychological illness or other condition.
- 11) Pregnant or planning to be pregnant during the trial period.

The eligibility criteria were more restrictive at the start of the trial. In an attempt to improve recruitment, protocol amendments on 8 March 2012 removed one inclusion criterion (The person has been receiving dialysis for more than 3 months but less than 36 months at the time of signing the consent form) and one exclusion criterion (Aged 75 or older at the time of signing the consent form).

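### The proportion of screened patients eligible for run-in (outcome 3b) is planned as one figure across the March 2012 widening of the entry criteria, and no numeric recruitment rate is specified for either period

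*SAP*

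**What the plan says.** Section 4.1 lists the logistics outcomes among the primary ones: recruitment rate as a number per month (3a), the proportion of screened patients eligible for run-in (3b), and the proportion of those eligible who enter run-in (3c). Section 2.1 gives their purpose, which is to inform the design of a larger clinical end-point study.

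On entry criteria, section 3.2.2 says "The eligibility criteria were more restrictive at the start of the trial", and then "In an attempt to improve recruitment, protocol amendments on 8 March 2012 removed one inclusion criterion" together with one exclusion criterion. The two restrictions removed were a window on time since starting dialysis (more than 3 but less than 36 months) and the exclusion of people aged 75 or older. That section mentions no restriction being added.

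On analysis, section 6.3.3 says of 3b and 3c: "Proportions and 95% confidence intervals for screened patients eligible for run-in and eligible patients who entered run-in will be estimated as described above". The method referred to, in 6.3.1, is a binomial generalised linear model with an identity link and an intercept only. For 3a, the same section says "Recruitment rate will be represented graphically by plotting monthly recruitment and cumulative recruitment numbers at each month of active recruitment".

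In section 8, Figure 1 shows monthly and cumulative enrolment, Table 2 gives enrolment by centre, and Table 9 gives numbers and percentages for the primary outcomes. None of the listed tables is described as split by criteria period.

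**The concern.** The word eligible defines the numerator of 3b and the denominator of 3c, and its meaning changed part-way through recruitment. The SAP was written in 2014, describes the change and gives its purpose, but carries nothing of it into the analysis. A planner of the larger trial needs to know what fraction of screened patients would qualify under a stated set of criteria. A single proportion over both periods does not answer that for either set, and its confidence interval refers to no clearly defined population.

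The recruitment rate has a smaller gap. It is defined as a number per month, but its only specified analysis is a plot. Sections 1.2 and 3.3 give slow recruitment as a reason for stopping early, so a stated rate for each criteria period would be among the more useful results of this study.

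**Working it through.** **The plan's own figures.** The SAP states no numerical target for 3a to 3c. Its nearest figures, in section 3.3, reproduce. For 70% of 150, 0.70 ± 1.96 × √(0.70 × 0.30 / 150) gives 62.7% to 77.3%, against the stated 62.5% and 77.5%. Also 72/150 = 48%, as stated.

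**Time under each set of criteria.** Section 1.2 says that the study "began recruiting patients on 16 May 2011 and stopped recruiting on 28 February 2013", and section 3.2.2 dates the change to 8 March 2012.

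- Before: 16 May 2011 to 8 March 2012 = 297 days = 9.76 months (at 30.4375 days per month).
- From: 8 March 2012 to 28 February 2013 = 357 days = 11.73 months.
- Total: 654 days = 21.49 months. Share before: 297/654 = 45.4%.

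Neither period is negligible.

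**What the pooled 3b estimates.** Let p1 and p2 be the eligible proportions before and from the change, and f the share of screened patients who were screened before it. An intercept-only model estimates

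pooled = f × p1 + (1 − f) × p2, so pooled − p2 = f × (p1 − p2).

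For a fixed screened population, removing restrictions cannot lower the number eligible. Then p1 ≤ p2 and the pooled value is at or below p2. The SAP gives none of f, p1 and p2, so the following values are assumptions that only show how the formula behaves:

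| p1 | p2 | f | Pooled | Pooled − p2 |
|---|---|---|---|---|
| 20% | 30% | 0.30 | 27.0% | −3.0 points |
| 20% | 30% | 0.47 | 25.3% | −4.7 points |
| 20% | 30% | 0.60 | 24.0% | −6.0 points |
| 30% | 25% | 0.30 | 26.5% | +1.5 points |
| 30% | 25% | 0.60 | 28.0% | +3.0 points |

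The last two rows could arise only if screening practice or case mix also changed.

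**Outcome 3c.** Pooling mixes two denominators in the same way. Nothing in the SAP says whether the newly eligible patients (older, or newer to or longer on dialysis) were more or less likely to enter run-in, so the sign is open.

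**Recruitment rate.** Section 1.2 reports: "In total, 88 participants from 11 sites were consented into the study". It adds "72 participants from 9 sites entered the run-in phase and 49 participants from 8 sites were randomised". The whole-period averages are 88/21.49 = 4.10 consented, 72/21.49 = 3.35 entering run-in and 49/21.49 = 2.28 randomised per month. The SAP does not give the split of the 88 by period. Over a range of assumed splits:

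| Share of the 88 consented before 8 March 2012 | Rate before (per month) | Rate from (per month) |
|---|---|---|
| 20% | 1.80 | 6.00 |
| 40% | 3.61 | 4.50 |
| 45.4% | 4.10 | 4.10 |
| 60% | 5.41 | 3.00 |

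The overall average is below the later rate only if fewer than about 40 of the 88 (0.454 × 88 = 40.0) consented before the change.

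**The case against.** Much can be said for the plan. Recruitment is to be plotted month by month, and section 3.2.2 dates the amendment, so anyone can look for a change in pace. Table 2 shows enrolment by centre. Table 9 promises numerical reporting of the logistics outcomes, and Table 1, on why screened patients were not consented, may show how many were lost to the two removed criteria. Simple binomial intervals are a reasonable descriptive choice in a feasibility study, and the Preface allows labelled supplementary analyses.

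Most of this stands, and it rules out three stronger readings.

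- A reader might infer that recruitment itself is pooled over time and sites. The monthly plot and Table 2 show otherwise. What is missing is a stated rate by period.
- A reader might infer that the pooled figures understate what the wider criteria deliver, and put a percentage on it. That needs an assumed rise in recruitment, applied to a whole-period average that the SAP never specifies. The tables above show that the sign can go either way.
- A reader might want intervals for 3b and 3c adjusted for clustering by site. The SAP gives 11 sites that consented patients but not the number that screened them, and cluster-adjusted intervals from so few sites are themselves unreliable.

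The case for the plan does not reach 3b. Neither Figure 1 nor Tables 1, 2 and 9, as listed, separate the eligible proportion by the criteria in force.

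**Conclusion.** The point holds for 3b: it is planned as one proportion over two definitions of eligible, with 45% of recruitment time under the narrower one. It extends to 3c through the denominator. That the pooled 3b is a mixture follows from the text, provided that screening took place in both periods. That it lies at or below the wider-criteria value rests on unchanged screening practice and case mix. Its distance from that value cannot be computed from the SAP. For 3c and the recruitment rate, not even the direction can be determined. For 3a the gap is limited to the absence of a numeric rate, overall or by period. This is an inexpensive improvement to the reporting of primary feasibility outcomes. It is not an error that invalidates the study.

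**What to change.** Add to section 6.3.3, and reflect in Table 9:

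*Outcomes 3b and 3c will be reported with 95% confidence intervals separately for the period before and the period from 8 March 2012 (or each site's date of implementing the amendment, where held), and overall. The recruitment rate will be reported as a number per month with a Poisson 95% confidence interval for the same periods and overall, stating whether it counts participants consented, entering run-in or randomised. These summaries are descriptive. No test between periods is planned.*

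Mark the amendment date on Figure 1.

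The change needs dates of screening, eligibility and consent, and no treatment allocation. The SAP does not say whether site implementation dates are held, so 8 March 2012 is the fallback. The cost is wording, a few extra table rows and wider intervals within each period. As a guide, 72 of 88 consented participants (81.8%) entered run-in. This is not 3c, but it is of a similar kind. Its Wald half-width is 1.96 × √(0.818 × 0.182 / 88) = 8.1 points. With half as many participants (44) it is 11.4 points.

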## 6.4 Analysis of secondary outcomes

All randomised participants with outcome data will be analysed according to the Intention-to-Treat (ITT) principle. The full analysis set will exclude randomised participants who withdrew from the study before any follow-up data on BNP or EQ5D was collected. BNP and EQ5D will be separately analysed using a linear mixed model with treatment group and baseline measurements as fixed effects and participant identifier and study visit as random effects. If there is insufficient data to reliably estimate random effects, the BNP and EQ5D data will be analysed using analysis of covariance (ANCOVA). Separate analyses will be performed on data from the 6 and 12 month visits. In all analyses, the effect of intervention group on outcome will be adjusted for baseline measurements. In addition, a logistic regression model will be used to predict successful completion of run-in (no, yes) from baseline BNP measurements.

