### **3.4 Treatment allocation**

Participants who tolerated a twice daily 6.25 mg dose of carvedilol by the end of the run-in phase were randomised 1:1 to one of the two treatment groups. Randomisation was conducted using an interactive voice response system (IVRS). The IVRS randomised patients by an adaptive allocation algorithm designed to minimise study site and dialysis modality (haemodialysis or peritoneal dialysis) imbalance within the two treatment groups.

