## 8.3 Planned figures

The following are planned summary figures:

- Figure 1. Monthly and cumulative enrolment
- Figure 2. Flowchart of patient progression through the study
- Figure 3. Proportions of participants on each dose of study drug (6.25 mg, 12.5 mg, 25 mg) by treatment group across titration and follow-up visits
- Figure 4. BNP over time (baseline, F6, F12) by treatment group for randomised participants
- Figure 5. EQ5D over time (baseline, F6, F12) by treatment group for randomised participants

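### The BNP and EQ5D model treats study visit as a random effect with only two levels, does not fix which analysis gives the 6- and 12-month effects, and omits both minimisation factors

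*SAP*

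**What the plan says.** SAP section 6.4 specifies for BNP and for EQ5D a "linear mixed model with treatment group and baseline measurements as fixed effects and participant identifier and study visit as random effects". Treatment and baseline are the only fixed effects. The fallback reads "If there is insufficient data to reliably estimate random effects, the BNP and EQ5D data will be analysed using analysis of covariance (ANCOVA"). Section 6.4 then says that the month 6 and month 12 data will be analysed separately, without saying whether by the mixed model, by ANCOVA or in addition to both.

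The schedule in section 3.6 measures BNP and EQ5D after baseline at F6 and F12 only. Section 8.3 agrees: "Figure 4. BNP over time (baseline, F6, F12) by treatment group for randomised participants" and "Figure 5. EQ5D over time (baseline, F6, F12) by treatment group for randomised participants".

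The SAP's other repeated-measures model, for dose in section 6.3.3, has "study visit as a fixed effect in the model and participant identifier as a random effect".

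Section 3.4 describes an "adaptive allocation algorithm designed to minimise study site and dialysis modality (haemodialysis or peritoneal dialysis) imbalance". Neither factor is in the section 6.4 model.

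**The concern.** Months 6 and 12 are two scheduled times chosen by design, not a sample from a population of visits, and two levels carry almost no information about a variance. That leaves three things unsettled.

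- **What is estimated.** With no visit or treatment-by-visit fixed effect, the mixed model gives one treatment effect pooled over visits. ANCOVA at a single visit gives an effect specific to that visit. A reader cannot tell how many treatment effects per outcome are planned, or which is the main one.
- **Which method is reported.** The condition "If there is insufficient data to reliably estimate random effects" has no threshold. With a two-level random factor, a variance estimate of zero is an ordinary result, and an analyst could reasonably take it either as meeting the condition or as harmless.
- **Precision.** Allocation was balanced on site and modality. If either predicts outcome after baseline adjustment, a model without it reports a standard error that ignores that balance.

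At stake are pre-specification and precision for the two secondary treatment comparisons. No primary outcome is affected.

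**Working it through.** The SAP states no standard deviation, effect size or power for BNP or EQ5D, so there is no figure of the plan's own to reproduce.

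**Inputs from the SAP.** Follow-up visits: 2 (sections 3.6 and 8.3). Randomised: 49 participants from 8 sites, 1:1 (sections 1.2 and 3.4). The analysis set is at most 49, because those who withdrew before any follow-up BNP or EQ5D are excluded (section 6.4).

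**Assumptions.** n = 44 to 49 measured at both visits. In the simulations, participant and residual variances are 0.5 each. Modality explains R² = 10-20% of the variance left after baseline, with balanced allocation.

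**1. Precision of the visit variance.** Two levels give 1 df. Multipliers of the estimate for 95% limits, treating the visit mean square as dominated by the visit variance:
- lower: 1/χ²(0.975; 1 df) = 0.20
- upper: 1/χ²(0.025; 1 df) = 1,018

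**2. How often it is zero.** With complete data the REML estimate is zero when the visit F-ratio is below 1.
- Equal visit means: P(F(1, n−1) < 1) = 0.68 for n = 44 and for n = 49.
- Random visit effect with SD r times the residual SD, n = 44: P(F(1, 43) < 1/(1 + 44r²)). For r = 0.2 the bound is 1/2.76 and the probability 0.45. For r = 0.5 it is 1/12 and 0.23.
- Fixed difference of d residual SDs, n = 49 (non-central F, non-centrality 49d²/2): 0.48 at d = 0.2 and 0.07 at d = 0.5.

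Zero is therefore the likeliest result with no drift between visits, and uncommon with a shift of half a residual SD.

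**3. Effect on the treatment estimate.** REML fits with visit random and with visit fixed were compared (n = 49, 250 simulated datasets per scenario).
- Complete data: the estimates agree to within rounding error, and the mean standard error is 0.247 for both.
- 25% missing at month 12: the estimates differ by at most about 0.02, on a standard error of about 0.26.

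**4. Separate visits.** A mixed model fitted to one visit has one response per participant. Participant and residual variance then enter only as their sum (2 parameters, rank 1) and cannot be separated. Visit-specific results therefore need either ANCOVA or a joint model with a treatment-by-visit term, and section 6.4 does not say which.

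**5. Omitted modality.** With balanced allocation the reported standard error is 1/√(1−R²) times too large, and the true size of a nominal 5% test is 2(1−Φ(1.96/√(1−R²))).

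| R² (assumed) | SE reduction if included, 1−√(1−R²) | SE ratio if omitted | True size if omitted |
|---|---|---|---|
| 10% | 5% | 1.05 | 3.9% |
| 20% | 11% | 1.12 | 2.8% |

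**The case against.** The case for leaving the model alone is that the visit variance is a nuisance parameter. The treatment effect survives (step 3), and a zero visit variance only reduces the model to a participant random intercept, which is usable. The stated objective is carvedilol against placebo on change from baseline, and a pooled effect answers that. This stands, and it limits the point to specification and precision.

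Several stronger readings are tempting but not supported.

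- **That the model cannot be estimated.** Only the visit variance is affected. A random visit slope per participant would be unidentified (4 covariance parameters for 3 observable moments), but the SAP mentions no slope.
- **That 68% is the chance of switching to ANCOVA.** The SAP speaks of insufficient data and does not name a zero variance as the trigger. The figure is how often the estimate is zero. Nor does such a trigger favour an arm: in 30,000 simulated null datasets (n = 49, no baseline covariate), the pooled and 12-month tests had sizes of about 5% whether or not the variance was zero.
- **That no 6- and 12-month effects are planned.** Section 6.4 plans separate analyses at both visits. What is missing is the method and the main time point.
- **That section 6.3.3 contradicts section 6.4.** The dose model estimates a proportion at each of many visits within each arm, so visit has to be fixed there. It shows the usual structure was available, no more.
- **That omitting the minimisation factors biases the result or inflates type I error.** It makes the test conservative, and only if the factors are prognostic after baseline. The SAP gives no figure for that, and the gain could be near zero.

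**Conclusion.** The point holds as a fault of specification. Visit is a poor random effect with two levels: 1 df, limits of about 0.2 to 1,018 times the estimate, and a zero estimate in about 68% of datasets when the visit means are equal (n of 44 to 49 assumed; fewer zeros if the means differ). The pooled treatment effect is essentially unaffected. What needs repair is that the model has no term for the 6- and 12-month effects, the separate analyses are not tied to a method, and the ANCOVA switch has no objective criterion.

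Leaving out dialysis modality costs 5-11% in standard error if it explains 10-20% of the variance left after baseline. That range is an assumption, and the error is on the conservative side. Site raises the same question and also needs a stated answer.

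These are secondary outcomes of a feasibility study whose target was set on run-in tolerability (section 3.3). The change should be made, but the trial's main conclusions do not depend on it.

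**What to change.** Before unblinding, replace the model in section 6.4 with a linear mixed model for the month 6 and month 12 values:

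- Fixed effects: treatment, visit, treatment-by-visit, baseline value and dialysis modality (HD or PD).
- Unstructured 2x2 within-participant covariance, with compound symmetry only if that model does not converge.
- Treatment differences at 6 and at 12 months both reported from this one model, with one named in advance as the main time point.
- A sentence on how site is handled. Eight sites take 7 df as fixed effects among at most 49 participants, so leaving site out with a stated reason is defensible.
- The insufficient-data switch to ANCOVA deleted, and the separate-analyses sentence replaced by the visit-specific differences above.

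The cost is a few lines of SAP wording, 1 df for modality and a few for the visit terms. The method is standard, and no new data are needed.

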### 6.6.2 Intradialytic hypotension

The incidence rate of intradialytic hypotension during run-in will be estimated using an intercept-only Poisson regression model. A Poisson regression model with treatment group as a covariate will be used to compare incidence rates for intradialytic hypotension in the randomised carvedilol and placebo groups.

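### Allocation was minimised on site and dialysis modality, but the BNP and EQ5D comparisons adjust only for baseline; if those factors are prognostic, the intervals are slightly too wide

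*SAP*

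**What the plan says.** SAP section 3.4 states that participants who tolerated run-in "were randomised 1:1 to one of the two treatment groups", using an "adaptive allocation algorithm designed to minimise study site and dialysis modality (haemodialysis or peritoneal dialysis) imbalance within the two treatment groups". Section 1.2 gives the size reached: "49 participants from 8 sites were randomised".

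Section 6.4 sets the only two secondary treatment comparisons, BNP and EQ5D. The main model is a "linear mixed model with treatment group and baseline measurements as fixed effects and participant identifier and study visit as random effects". If the random effects cannot be estimated reliably, ANCOVA takes its place. In all these analyses "the effect of intervention group on outcome will be adjusted for baseline measurements". Site and modality are not mentioned there. They reappear only in section 8.1, where Table 3 describes the stratification variables by arm. No reason is given for leaving them out of the models.

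The exploratory comparison in section 6.6.2 also names treatment as its only covariate ("A Poisson regression model with treatment group as a covariate will be used to compare incidence rates for intradialytic hypotension"). It is noted for completeness; the figures below concern BNP and EQ5D.

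**The concern.** Forcing the arms to be alike on a factor removes that factor's contribution to the chance difference between arms. A model that omits the factor does not know this. It leaves the factor's variance in the residual and reports a standard error larger than the true sampling variability. The interval then covers more often than its nominal 95%, and the test rejects less often than 5% under no effect. With 49 randomised, and fewer analysed because section 6.4 excludes those with no follow-up data, precision is scarce. Analysing by a factor that the allocation already used is normally a cheap way to keep some of it.

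**Working it through.** **Inputs from the SAP.** 49 randomised, 8 sites (49/8 ≈ 6 per site), 1:1 allocation, balancing on site and modality (HD/PD), adjustment for the baseline value only.

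**Inputs not in the SAP, assumed.** Share of post-baseline outcome variance explained by modality: 0–10%. Share explained by site: 0–30%. 25% on PD. Uneven site sizes. Probability of assigning the balancing arm: 0.8 or 1.0.

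**The plan's own figure.** There is no power or precision figure for BNP or EQ5D. The one design calculation is for run-in tolerability (section 3.3): 0.70 ± 2 × √(0.70 × 0.30/150) = 0.70 ± 0.075, or 62.5% to 77.5% as stated (62.7% to 77.3% with 1.96). The present point does not depend on it.

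**By hand, modality only.** Let s be the share of post-baseline variance due to modality, and suppose modality is exactly balanced by arm.

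- Variance reported by the baseline-only model: σ²(1/n₁ + 1/n₂). True variance: (1 − s)σ²(1/n₁ + 1/n₂).
- Ratio of adjusted to unadjusted width ≈ √(1 − s), apart from one degree of freedom (49 − 3 = 46 becomes 45).
- s = 5%: √0.95 = 0.975, so 2.5% narrower. s = 10%: √0.90 = 0.949, so 5.1% narrower.
- Size of the baseline-only nominal 5% test, large-sample: s = 5%, 1.96/0.975 = 2.01, about 4.4%; s = 10%, 1.96/0.949 = 2.07, about 3.9%.

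**By simulation.** 4,000 trials per scenario with no treatment effect, N = 49, minimisation over 8 sites and 2 modalities, single-visit ANCOVA with and without the factors. Ranges span the two assignment probabilities. The Monte Carlo standard error of coverage is about √(0.05 × 0.95/4000) = 0.3 points.

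| Share explained (site + modality) | Coverage, baseline only | Width if modality added | Width if modality and 7 site indicators added |
|---|---|---|---|
| 0% + 0% | 94.5–95.3% | 0.1–0.3% wider | 3–5% wider |
| 5% + 5% | 95.8–95.9% | about 2.5% narrower | 1–3% narrower |
| 10% + 10% | 96.8–96.9% | about 5% narrower | 6–8% narrower |
| 20% + 10% | 96.5–97.6% | about 5% narrower | 11–13% narrower |
| 30% + 10% | 97.5–97.8% | about 5% narrower | 17–19% narrower |

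At 20% + 10% with deterministic minimisation, the baseline-only model reports a standard error of 0.284 against a true sampling SD of 0.246. With assignment probability 0.8 the true SD is 0.258, so looser balance means less conservatism. N = 40 gives the same pattern: adding both factors ranges from 4–7% wider to 16–18% narrower. A further simulation with 46 analysed gave a modality cost of 0.2–0.3% in width if it is not prognostic, and a gain of about 2% or 5% at shares of 5% or 10%. The modality column agrees with the hand calculation.

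**The case against.** The strongest reply is that the harm is conditional and small. BNP and EQ5D are already adjusted for their own baseline, which may carry most of what modality or site would predict. With no prognostic share the planned analysis has its nominal coverage, and below about a 10% combined share the loss is negligible. This stands, and it limits the point.

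A reader might infer that the planned intervals are certainly too wide, or by a lot. Modality shifts of 1.0 or 1.5 residual SD, with 20–40% on PD, would widen the unadjusted interval by 8–12% or 18–25%. Converting shift d and PD share q to a variance share by d²q(1 − q)/(1 + d²q(1 − q)), those shifts require modality alone to explain 14–19% or 27–35% of the post-baseline variance. Nothing in the SAP supports that. A 0.5 SD shift corresponds to 4–6%, and 2–3% in width.

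It is also tempting to require a site term. Seven site indicators widen the interval if site is not prognostic. A random site intercept, dropped when its variance is estimated as zero, fares no better. In 1,500 simulated trials per scenario (46 analysed, site + modality shares of 0 + 0% to 10 + 10%), site was dropped in 29–60% of trials. The test rejected in 5.9–6.7% with Wald inference and 4.9–6.1% with a t reference (Monte Carlo standard error about 0.6 points). It would also put a random effect into the ANCOVA that section 6.4 keeps for when random effects cannot be estimated.

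Finally, the term baseline measurements might be read as covering modality. In section 6.4 it refers to the BNP and EQ5D values; dialysis regimen appears in section 6.2 only as a descriptive characteristic.

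**Conclusion.** The omission is real and its direction is clear: the planned BNP and EQ5D analysis is correct or mildly conservative. In no simulated scenario did the baseline-only interval clearly under-cover, so a reader should not infer an inflated false-positive rate.

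For modality, the size runs from about 0.3% in width lost by adjusting to about 5% gained, on the assumption that it explains 0–10% of post-baseline variance. The possible gain from site is larger only if site explains a large share (11–19% narrower with both factors at site shares of 20–30%), and the SAP gives no ground for assuming that. The figures are for a single-visit ANCOVA, which matches the separate 6- and 12-month analyses. In the mixed model, modality would act on the between-participant variance in the same direction.

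Severity is low. The primary feasibility outcomes in section 6.3 are proportions, rates and counts with no test between arms, and are unaffected. The case for changing the plan is that adding modality costs almost nothing.

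**What to change.** In section 6.4, add dialysis modality (HD/PD, as used in the allocation) as a fixed effect in the linear mixed model and in the fallback ANCOVA, for both BNP and EQ5D. Do not require site in the main model. Either state the reason (8 sites, about 6 participants each), or report a site-adjusted model as a sensitivity analysis.

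The cost is one or two sentences of SAP text and one degree of freedom. No new data are needed: modality was used for allocation, and dialysis regimen is already tabulated under section 6.2. Section 5.2 holds back unblinded analysis until the SAP is approved, so the change belongs before that step. If unblinding has already taken place, report the modality-adjusted result as an unplanned supporting analysis, as section 5.2 provides.
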